6.2 SECONDARY OBJECTIVES

- 1) To estimate the impact of time of initiation of antiretroviral therapy on short- and long-term clinical and laboratory outcomes.
- 2) To evaluate the correlation between gastrointestinal dysbiosis and systemic immune activation in MSM with HIV and alcohol use disorders.
- 3) To evaluate the association with alcohol abuse and timing on ART initiation neurocognitive function and neuro inflammation in MSM with acute and recent HIV.
- 4) To determine whether NNRTI and INSTI-based ART regimens have differential effects on time to HIV VL suppression and size of the latent HIV reservoir.
- 5) To determine whether NNRTI and INSTI-based ART have differential moderation of immune activation associated with HIV and alcohol abuse.

7. STUDY DESIGN

[figure not shown]
7.1 GENERAL STUDY DESIGN

This protocol for the MERLIN study describes the extended follow-up of participants enrolled in the *SABES* study, a study of ~250 HIV+ MSM and TGW in Lima, Perú. In this study, we will enroll up to 25 individuals with acute HIV infection.

The *SABES* study: The ongoing *SABES* study combines laboratory and epidemiologic data with

modeling to investigate the hypothesis that early ART initiation and management of alcohol use disorder will prevent onward HIV transmission among MSM/TGW diagnosed with acute (FI-FII: Ab-/HIV RNA+) or recent (≤ 3 months) HIV infection (FIII-V). The SABES study population is MSM and transgender women (TGW) not using feminizing hormones (all referred to as "MSM" from here on) in Lima. This study is being conducted in 3 phases: 1) HIV screening, 2) monthly follow-up testing of HIV-uninfected participants by point-of-care EIA and NAAT testing for HIV RNA in pools of seronegative specimens (pools are run daily), and 3) enrollment of MSM with incident HIV infection into a randomized ART treatment study (Figure 1). Only participants with acute (seronegative but HIV RNA+) or recent HIV infection (EIA+ with a prior HIV-negative test within 3 months) are eligible for enrollment in the treatment phase of the SABES study. These participants are stratified by acute vs. recent infection and randomized 1:1 to Immediate arm (to receive ART immediately) or Deferred arm (to receive ART beginning at 24 weeks or when the participant meets Peruvian treatment initiation thresholds, whichever comes first) (Figure 1). We completed enrollment of 225 HIV+ participants into the SABES study by the end of March 2016. A small number (5-10) of additional participants will be enrolled in SABES; those with symptomatic acute HIV infection will receive ART immediately, in accordance with current Peruvian treatment guidelines and will therefore not be randomized to possibly delay ART. The Human Subjects section contains a discussion of risks and benefits. All SABES participants received either EFV/FTC/TDF or EVG/COBI/FTC/TDF as first line medication. Virologic suppression at 48 and 96 weeks is equivalent for both regimens when used as initial treatment [48]; however because EVG/COBI/FTC/TDF may result in more rapid viral suppression we began using EVG/COBI/FTC/TDF for new participants when it became available as a donated drug in late 2015.

Specimen collection: The MERLIN study involves laboratory analysis of specimens collected during the 48-week SABES study as well as during the MERLIN study, through 2022 (about 5 years after MERLIN enrollment). Visits with specimen collection occurred in the SABES study at 1, 2 and 4 weeks after ART initiation (study weeks 1, 2, 4 for the Immediate arm and weeks 25, 26, 28 for the Deferred arm); additional visits occur at 8, 16, 24, 32, 40 and 48 weeks. Extensive samples, including blood, stool for microbiome, and dried blood spots and hair for drug and alcohol tests were collected at each study visit for SABES study participants, starting at participant number 110. In addition, during the latter half of the SABES study, neurocognitive testing was conducted starting at participant 110, as well as collection of cerebrospinal fluid (CSF) by lumbar punctures on a subset to investigate the early neurologic impact of HIV infection. For the MERLIN study, we will collect blood, urine, rectal secretions and rectal biopsies, and stool specimens every 24 weeks throughout 2022, as well as additional neurocognitive testing and collection of CSF on a subset of participants.

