Design: The MERLIN Study extends the follow-up of participants enrolled in the SABES Study, a study of ~250 MSM and TW in Lima with acute and recent HIV infection enrolled in an early vs. deferred antiretroviral treatment study. The MERLIN study will offer follow-up to all of the patients enrolled in the SABES study, prioritizing the participants who also were enrolled in a related Observational Study, in which baseline peripheral blood mononuclear cell (PBMC) isolation sampling was conducted. Additionally to the participants previously enrolled in SABES, up to 25 additional participants with acute HIV diagnosis will be enrolled directly in this study and will be treated immediately upon diagnosis.

Consenting eighteen-year old or older MSM and TW, who participated and received ART in the SABES Study and who have acceptable hematologic, liver, and renal function will be considered to participate in the MERLIN study, in which they will continue a 3-drug ART regimen.

Because of the low number of participants, which acute infection who received immediate treatment in the SABES study and who could be eligible for MERLIN, a new enrollment and follow-up cohort will be open with up to 25 participants (see above). In this cohort, participants with acute HIV infection will initiate antiretroviral treatment immediately after receiving diagnosis and will also be followed up for an extended time.

Duration: Up to 5 years from enrollment on this protocol (through 2022) with visits timed referencing date of HIV diagnosis and original SABES study visits (or SABES enrollment if applicable).

Treatment Regimen:

In *SABES* Step 3, participants had been randomized to either one of the following arms: Immediate Arm: to immediately receive ART for 48 weeks; or Deferred Arm: to delay treatment for 24 weeks (unless Peruvian criteria for initiation of treatment are met), and then receive ART at 24 weeks.

For the purposes of correlative studies, participants in the Immediate Arm are further categorized as initiating Immediate ART (in Acute HIV: Fiebig I/II) or Early ART (Recent HIV: Fiebig III/V) infection.

The MERLIN participants will initiate the co-formulation EVG/COBI/FTC/TDF (Genvoya) for its component TAF.

EVG/COBI/FTC/TDF is not readily available in private or public sector HIV care in Peru, but it is considered acceptable based on FDA-approval and US-based HIV guidelines to the Peruvian Ministry of Health (MOH).

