changes, and decrease seeding of the reservoir. Initiation of ART in FI-II will have the greatest benefit. CD4 counts and peripheral inflammatory markers in the FIII-V group and the group treated at 24 weeks will approach those in the FI-II group at 1.5 and 3.5 years after ART initiation; in contrast, changes in the GI microbiome and the HIV reservoir over time will be more modest. 2. Irrespective of the time of ART initiation, alcohol use will compound the negative effects of HIV to generate greater levels of dysbiosis, microbial translocation, up-regulation of inflammatory pathways, and seeding of the HIV reservoir.

Specimens from the *SABES* and *MERLIN* studies will be used for a series of laboratory investigations probing the mechanisms by which early treatment reduces the HIV reservoir and HIV-associated inflammation, and seeking to determine how soon after HIV acquisition ART must be initiated to confer these beneficial effects. The most in-depth studies will prioritize participants enrolled during the latter half of the *SABES* study who had large PMBC collections at the time of HIV diagnosis and throughout follow-up. These include the following 3 groups based on time of ART initiation: a) *Immediate*: during FI-II (N~20), b) *Early*: during FIII-V (N~35) or c) *Deferred*: at 24 weeks after diagnosis (N~55). A small number of additional studies may be conducted on all participants in the *SABES* study: a) *Immediate*: during FI-II (N~35), b) *Early*: during FIII-V (N~72) or c) *Deferred*: at 24 weeks after diagnosis (N~115). The *MERLIN* study will assess outcomes after 1.5 and 3.5 years after initiation of ART in these MSM and TGW. The results will be evaluated every 6 months during the follow-up of the participants in the study (up to the end of 2022). Laboratory analyses will be conducted in Lima, Perú and Seattle, WA as well as in the laboratories of our collaborators at University of California, San Francisco (UCSF) and University of Montreal (UoM). Additional neuropsychiatric and biologic data will be collected to evaluate neuroinflammation and cognitive changes in early HIV infection (collaborators at UCSF, Yale, and UNC).

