6.1 PRIMARY OBJECTIVES

- 1) To determine the relative long-term benefits of immediate vs. early vs. deferred initiation of ART.

Initiation of ART during Fiebig I-II, while theoretically appealing, is currently infeasible in clinical practice because the duration of FI-II is very short (10 days) and because antibody-based tests, used almost world-wide, are unable to diagnose FI-II. Six months of ART initiated shortly after seroconversion (FIII) can improve many immune parameters, although not to the near normal level seen when ART is initiated during FI-II [3]. Longer-term follow-up of seropositive participants who started ART ~2-8 months after HIV acquisition compared to those initiating ART during FI-II is needed to see whether markers of inflammation and residual viral load might continue to improve after 6 months, decreasing the difference between the groups. Methods: We will evaluate the 3 groups using specimens from equivalent times after ART initiation through the first 5 years of ART usage, comparing CD4 counts, time to undetectable VL, GI microbiota, and inflammatory markers. The size of the replication-competent HIV reservoir in PBMCs will be compared using measurements of multiply spliced viral RNA (msRNA) and the degree of low-level infection of new cells by assessing the production of circular viral DNA (2LTR HIV DNA). We will model the size and persistence of the viral reservoir across all ART-adherent study participants. In a subset of individuals from each group, the proviral integration sites will

be defined at ART initiation and after 1.5 and 3.5 years to assess the maintenance of the reservoir by proliferating CD4 cells. We will continue evaluating endpoints annually or biannually, as long as participants remain on study.

- 2) To determine the impact of high-level alcohol use on the relative long-term benefits of immediate vs. early vs. delayed ART initiation

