10.3.2. Follow-up Assessments

10.3.2.1 Participants from SABES step 3

The MERLIN study visits should occur at 24-week intervals with respect to SABES enrollment, rather than with respect to MERLIN enrollment in order to preserve time-points with respect to date of SABES enrollment and ART randomization

If the participant received MOH-based ART after completing SABES, the study visit schedule should resume a 24-weekly schedule with respect to timing from SABES enrollment, at the next possible visit (e.g. 72, 96, 120, etc., weeks).

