10.3.4.13 Rectal Biopsies and Rectal Secretions

Rectal biopsies will be performed in a subset of 60 participants who additionally consent, using a separate informed consent procedure, to up to 4-3 rectal biopsies. Rectal secretions will be collected via a swab or sponge at the time of biopsy. In Immediate arm participants, the biopsies will be performed at 96, 144 and 192; ; in the Deferred arm, biopsies will occur at 120, 168 and 216 weeks. Biopsy procedure will be performed following the SSP.

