Participants will be invited to participate in this procedure according to their antiretroviral treatment initiation condition and clinical evolution.

There is a separate **informed** consent. The qualitative and quantitative evaluation of HIV seeding (including its location in different CD4+ T cells subsets) will require a big number of cells, and it is important to learn about the size and distribution of the HIV reservoir, this is a key factor to induce a functional cure. Hence, we will use leukapheresis to collect a big number of cells at specific times (weeks 72, 120, 168 and 216 for the deferred arm and weeks 96, 144, and 192 for the immediate arm).

- **Section 10.3.4.14 Lumbar Puncture.** This section has been amended to increase the number of participants that could undergo the procedure, it now reads:

All the participants could be invited to undergo lumbar puncture. Based on operational and budget considerations it was initially considered to include only 40 participants for this procedure. However, we have lost participants who initially had accepted to undergo this

procedure, because they are no longer eligible to continue in the study or because they refuse to continue in the procedure for personal reasons.

This modification will allow replacement of participants who could have been lost to follow-up in MERLIN, and include additional participants who are eligible for these procedures. This will allow a more robust analysis at the late time points of the study.

Participants will be invited to participate in this procedure according to their antiretroviral treatment initiation condition and clinical evolution.

Those participants who accept the procedure will need to sign a specific informed consent; otherwise, no procedure could be performed. The evaluations will be done at specific visits indicated in the procedures table.

Amendment Letter N° 03

Date : December 1 2019

To : Protocol Research Team

From : Protocol Chair and Co-Chair

Topic : Amendment Letter N° 3 to Protocol MERLIN, Version 3.0, April 12 2018, entitled "Modulating the Impact of Critical Events in Early HIV Infection: Effect of ART Initiation and Alcohol use".

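### Rectal biopsy, leukapheresis and the last lumbar puncture fall at equal time on ART only if Deferred participants started at week 24, yet the protocol allows earlier starts

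*Protocol*

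**What the plan says.** Section 6.1, under Primary Objective 1, sets the basis of comparison: "We will evaluate the 3 groups using specimens from equivalent times after ART initiation through the first 5 years of ART usage". Amendment Letter 03 (Section 10.3.4.11) likewise places the main evaluation at years 2 and 4 after ART start.

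The Deferred strategy has an early exit. Section 7.1 has the arm "to receive ART beginning at 24 weeks or when the participant meets Peruvian treatment initiation thresholds, whichever comes first", and the Treatment Regimen text of the Executive Summary repeats the exception: "unless Peruvian criteria for initiation of treatment are met". Section 4.1, however, lists the Deferred group by time of ART start as simply "at 24 weeks after diagnosis (N~55" for the in-depth studies, with about 115 across all of SABES.

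The visit clock is enrolment, not ART start. Section 10.3.2.1: "The MERLIN study visits should occur at 24-week intervals with respect to SABES enrollment". Three procedures are then assigned by arm:
- Rectal biopsy (Section 10.3.4.13): "In Immediate arm participants, the biopsies will be performed at 96, 144 and 192", and "in the Deferred arm, biopsies will occur at 120, 168 and 216 weeks".
- Leukapheresis (Section 10.3.4.10 as amended by Letter 02): "weeks 72, 120, 168 and 216 for the deferred arm and weeks 96, 144, and 192 for the immediate arm".
- Last lumbar puncture (footnote 7 to the Section 10.1 table): week 240 for Immediate, week 264 for Deferred.

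Nothing in the protocol moves these weeks for a Deferred participant who started before week 24.

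**The concern.** The 24-week offset is evidently meant to equalise time on ART. For anyone who left deferral early it does not. That person is biopsied, leukapheresed or has CSF taken after more treatment than the Immediate-arm comparator, and after a shorter untreated period than the Deferred label implies.

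Early starters are also not a random subset, because they started on meeting treatment criteria.

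These samples are few and invasive: 60 participants were planned for biopsy and originally 40 each for leukapheresis and lumbar puncture. An analysis can adjust for actual time on ART, but it cannot recover a specimen that was not taken at the matching time. Each misaligned participant also counts for more in a small set. In the integration-site study (Section 14.6.5, about 15 per group, drawn preferentially from leukapheresis participants) one person is 1/15, or about 7% of a group.

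**Working it through.** **Inputs.** Immediate biopsy weeks 96/144/192 and Deferred 120/168/216 (10.3.4.13). Amended leukapheresis weeks are the same, plus Deferred week 72 (Letter 02). Last lumbar puncture 240 and 264 (10.1, footnote 7). Visit window 8 weeks either side (10.1). Deferred start week s, at most 24 (7.1). Immediate ART is taken to start at week 0. The protocol gives no distribution for s, so the values below are assumptions that span the range.

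**Step 1: reproduce the intended alignment.** Weeks on ART = study week - s. At s = 24:
- Biopsy and leukapheresis: 120 - 24 = 96, 168 - 24 = 144, 216 - 24 = 192.
- Last lumbar puncture: 264 - 24 = 240.

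All agree with the Immediate arm. The exception is leukapheresis at Deferred week 72 (48 weeks on ART), which has no Immediate counterpart in the amended schedule.

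**Step 2: let s vary.** Excess over Immediate = 24 - s at every arm-specific visit. The gap at the nearest existing 24-weekly visit is the smaller of s and 24 - s.

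| s | Weeks on ART at 120/168/216 | Excess (weeks) | Excess, % of 96/144/192 | Gap at nearest 24-weekly visit |
|---|---|---|---|---|
| 4 | 116/164/212 | 20 | 21/14/10 | 4 |
| 8 | 112/160/208 | 16 | 17/11/8 | 8 |
| 12 | 108/156/204 | 12 | 12.5/8/6 | 12 |
| 16 | 104/152/200 | 8 | 8/6/4 | 8 |
| 20 | 100/148/196 | 4 | 4/3/2 | 4 |
| 24 | 96/144/192 | 0 | 0/0/0 | 0 |

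The ceiling, approached as s nears 0, is just under 24/96 = 25% at the first point and 24/192 = 12.5% at the last. The excess is larger than the 8-week window when 24 - s > 8, that is, s < 16.

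**Step 3: group-level scale (assumption).** If a fraction p of the sampled Deferred participants started early, evenly over weeks 0 to 24, their mean excess is 12 weeks and the group mean excess is 12p: 0 weeks if none did, 1.2 at 10%, 4.8 at 40%. The mean shift may therefore be modest even where individual misalignment is large.

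**Step 4: which samples are exposed.** The Section 10.1 table puts PBMC, plasma, CD4/CD8, viral load, urine and repeat stool on one 24-weekly grid for both arms. For these, a specimen within 12 weeks of any target time on ART always exists, and the gap is above 8 weeks only for s between 8 and 16.

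**The case against.** The best reply is that most primary-endpoint material comes from the shared grid. The promise in Section 6.1 concerns which specimens are used, and a suitable one can be picked by actual time on ART. The early start is openly stated, the enrolment clock is a deliberate choice that preserves the randomised time-points, and analysis by time since ART may be set out in an analysis plan that is not shown. All of this stands, and it limits the point to the arm-specific procedures. It does not answer the point there, because those weeks are fixed in the protocol.

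Four stronger readings are tempting, and the protocol does not support them.
- *All Deferred sampling is misaligned.* The table in Section 10.1 shows otherwise.
- *The week 192/216 cut-off for PBMC and CD4 (Letter 03) loses matching data.* An early starter reaches 192 weeks on ART at week 192 + s, between weeks 192 and 216, and is still sampled at both.
- *The error favours the study's hypothesis.* Sections 4.1 and 5 expect convergence for CD4 counts and peripheral inflammatory markers, which are measured on the shared grid. For gut and reservoir they expect lasting differences, so dilution there would work against the hypothesis. Selection of early starters could act in either direction.
- *The excess reaches 24/78 = 31% at 1.5 years.* No arm-specific procedure is aligned to 78 weeks on ART; the first matched point is 96.

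**Conclusion.** The point holds for rectal biopsy, amended leukapheresis (leaving aside the extra Deferred week 72) and the last lumbar puncture. As written, the schedule delivers equal time on ART only for Deferred participants who started at week 24. An early starter is 24 - s weeks off, up to just under 25% at the 96-week point and 12.5% at the 192-week point. Starts from week 16 onward stay within the visit window.

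The overall effect cannot be sized, because the number and timing of early starts are not given and could be close to nil. The sign of any bias is uncertain. This is a modest, inexpensive correction to the schedule and to a group label. It does not undermine the main comparison.

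**What to change.** Add a footnote to the Section 10.1 table, cross-referenced in 10.3.4.10, 10.3.4.13 and 10.3.4.14. For Deferred participants who started ART before week 24, it would place the arm-specific procedures at the existing 24-weekly visit closest to the target weeks on ART, counted from the recorded ART start. This changes the visit only for starts before week 12 (for example, week 96 in place of 120) and cuts the largest mismatch from nearly 24 weeks to 12. Starts strictly between weeks 8 and 16 would still be more than 8 weeks off.

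State also that these specimens are matched or analysed by actual weeks since ART start. For samples already taken, that is the only part that can help. In Section 4.1, describe Deferred as ART 'by week 24'.

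Cost: a footnote and some wording. No procedure is added, and the rule for starting treatment is not touched. Section 10.3.4.2 already requires antiretroviral history in source documents. The downside is that sites must track an individual sampling week for a minority of Deferred participants.

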7.2 MANAGEMENT OF SUBJECTS WITH VIROLOGIC FAILURE OR PREMATURE DISCONTINUATION OF TREATMENT

Virologic failure is defined if there is an HIV-1 RNA of >400 copies/mL in 2 consecutive measurements after having reached an HIV-1 RNA level of <50 copies/mL in 2 consecutive measurements separated by at least 14 days.

If there is a sub-optimal virologic response, the Virologic Laboratory of the University of Washington will perform genotyping from a sample taken from before discontinuation of the treatment when the HIV-1 RNA is >500 copies/mL with the goal of determining if there has been development of resistance or not, and if yes, to help in the selection of a new antiretroviral regimen. The substituted regimen will be provided by the study while the participant is participating in the study. If the genotype does not reveal evidence of resistance and there are convincing arguments (that is to say, adherence has improved substantially or there were intercurrent illnesses that could explain the elevated viral load) the participant could continue with the original treatment plan. Any decision to continue with the regimen in the context of a suboptimal viral response must be discussed with the PI/co-PI of the study. The subsequent management of whether or not to initiate a new regimen or modify the regimen must be at the discretion of the local investigator in concordance with the standard of care. Subjects that remain in the study will be requested to complete all of the described evaluations during which time they will be provided an alternative antiretroviral treatment provided by the study.

